### Safety variables:

- Incidence of PNALD/PNAC: Number of patients in each treatment group with direct bilirubin levels > 2 mg/dL, confirmed by a second sample collected 7 days after the first sample (incidence of PNALD/PNAC). Time from Study Day 1 until reaching direct bilirubin levels > 2 mg/dL, followed up by a second sample collected 7 days after the first sample (time of developing PNALD/PNAC). (i.e., presented as the Study Day on which for the first time the direct bilirubin level was found > 2 mg/dL.)
- Sterols in plasma including phytosterols:  $\beta$ -sitosterol, campesterol, stigmasterol, brassicasterol, ergosterol, cholesterol, desmosterol, lanosterol,  $\beta$ -sitostanol, lathosterol, squalene (a sterol precursor).
- Laboratory values: (blood, plasma, or serum): triglycerides, direct bilirubin, total bilirubin, alanine aminotransferase (ALT), aspartate aminotransferase (AST), gamma-glutamyl transferase (GGT), alkaline phosphatase (ALP), creatinine, urea nitrogen, electrolytes (Na, K, Mg, Cl, Ca, Phosphate), trace elements (ferritin, Zn, Se, Cu, Mn, Cr), glucose, total protein, C-reactive protein (CRP), white blood cells (WBC), red blood cells (RBC), and platelet counts, hemoglobin (hgb), hematocrit (hct), international normalized ratio (INR).
- Vital signs: blood pressure, heart rate, body temperature.
- All adverse events (AEs).
- The relation between genetic polymorphisms in the fatty acid desaturase genes FADS1 and FADS2 and plasma concentrations of linoleic acid,  $\alpha$ -linolenic acid, arachidonic acid, docosahexaenoic acid, eicosapentaenoic acid, and Mead acid, as well as relation to EFAD (triene/tetraene ratio).

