## **Clinical Study Protocol SMOF-028-CP4**

### **Smoflipid® (lipid injectable emulsion)**

---

labelling, and dose of study drug is provided in Section 10.

The study population will be pediatric patients of 3 months to 16 years of age with indication for PN that is expected to continue for 90 days at minimum, as consequence of reversible or irreversible intestinal failure. This condition can be present in patients with, e.g., short bowel syndrome, intestinal atresia, abdominal surgical procedures due to gastroschisis or omphalocele closure, necrotizing enterocolitis, gastrointestinal motility disorder, or mucosal enteropathy. Study patients will be hospitalized or treated in the home care setting, and the study will also continue during transmission from hospital to home PN or during re-hospitalization. During the first 90 days, study treatment will last as long as PN is required to cover 60% or more of the patient's total energy requirement. Unless terminated in the first 90 days, study treatment will last as long as any PN including intravenous lipids is required, but at maximum for 1 year in total.

If a patient is found to be potentially eligible for participation in the study, a signed and dated informed consent form (ICF) will be obtained from the patient's parent(s) or legal representative(s) prior to the performance of any study-specific procedures or assessments. If possible, patient assent must also be obtained.

Randomization into the 3 age group cohorts will be distributed evenly so as to have 48 subjects in each age group with at least 23 subjects in each treatment group per cohort (see Section 6.3):

Randomization group 1: 48 patients 3 months to < 2 years of age

Randomization group 2: 48 patients 2 years to < 12 years of age

Randomization group 3: 48 patients 12 to 16 years of age

Before initiation of study treatment, demographics, including medical history, race and ethnicity, starting date and composition of current PN, current medications, physical examination findings, vital signs, body weight and length/height, BMI (> 2 years) and head circumference (< 3 years) will be documented, and blood samples will be obtained for the assessment of baseline laboratory values.

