### **7.2.2 Analysis sets**

#### **Safety Set**

The safety population will consist of all patients having received at least one dose of a study drug and at least one post-baseline safety evaluation. The safety population will be used for analysis of safety variables.

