### 7.2.3 Statistical Analysis

The study outcome measures were selected in order to assess the safety and nutritional efficacy of the PN lipid emulsion. No primary and secondary measures are defined. Outcome measures will be evaluated as they are documented. Laboratory values will be transformed into SI (Système International d'Unités) if necessary.

A comprehensive Statistical Analysis Plan (SAP), covering details of all methods used to analyze the various parameters will be prepared. It will also include information on the handling of missing values. The SAP will be reviewed, and if needed, updated before data analysis. The SAP will be approved and signed off prior to unblinding the study.

All target variables will be analyzed in an exploratory manner presenting descriptive statistics. Binary, categorical and ordinal parameters will be summarized by means of absolute and percentage numbers (including 'missing data' as valid category). Numerical data will be summarized by means of standard statistics (e.g., number of available data, mean, standard deviation, minimum, median, maximum, and lower and upper quartile). Confidence intervals (CI) will be determined within treatment for all outcome parameters for which mean and standard deviation will be calculated.

Wherever useful, the summary statistics will be presented by Study Day. Results will be presented stratified by study drug and age group, and overall. In addition, appropriate figures (e.g., bar charts, Box-Whisker-Plots) may be presented to summarize the results for some parameters also in a graphical way.

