### Early termination of study treatment (Before Study Day 91)

Patients who received study drug at least once (i.e., first study infusion was at least started) but who didn't complete at least 90 days of study treatment, will be counted as "late-drop-outs".

The study treatment will stop if infusion of the study drug cannot be continued because TG or direct bilirubin levels remain above the defined limits (see 10.3.4 Intravenous Lipid Dose Management). The study treatment will also stop if less than 60% of the patient's energy requirements need to be covered from PN for at least one week.

In case of early termination patients will undergo final examination. They will be replaced unless the decision to terminate was made for safety reasons. Patients who were withdrawn

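### Time to PNALD/PNAC is a Study Day that only cases have, follow-up is unequal, and the supplied text gives no rule for non-cases, so this one safety variable is hard to interpret

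*Combined protocol and SAP*

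**What the plan says.** Section 5.2 (Safety variables) lists two bilirubin variables in one bullet. The first is incidence, the number of patients per group with direct bilirubin above 2 mg/dL. The second is the time from Study Day 1 to that level, "presented as the Study Day on which for the first time the direct bilirubin level was found > 2 mg/dL".

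Section 7.2.3 treats every target variable descriptively. "Numerical data will be summarized by means of standard statistics", with the number of available values, mean, SD, median and quartiles given as examples, and confidence intervals within treatment. Results are to be shown by study drug and age group, and overall. The same section announces a SAP "covering details of all methods used to analyze the various parameters will be prepared", including the handling of missing values. The text of that SAP is not in the supplied document.

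Follow-up is unequal by design:
- For patients still on treatment after Day 90, 6.1 says: "study treatment will last as long as any PN including intravenous lipids is required, but at maximum for 1 year in total".
- Treatment can also stop before Day 91 (7.3). On patients who stop early, 7.3 says: "They will be replaced unless the decision to terminate was made for safety reasons".
- The safety set is "all patients having received at least one dose of a study drug and at least one post-baseline safety evaluation" (7.2.2), so treated early leavers with one evaluation stay in it alongside their replacements.

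The event is worded differently for the two variables. Incidence needs a value "confirmed by a second sample collected 7 days after the first sample (incidence of PNALD/PNAC"), whereas time needs one "followed up by a second sample collected 7 days after the first sample (time of developing PNALD/PNAC").

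**The concern.** A patient who never exceeds 2 mg/dL has no Study Day to summarise. If the variable is reported as a mean or median day, non-cases drop out and the figure describes only when the cases happened to be detected. With follow-up that varies between patients, that figure depends mainly on how long people were observed and very little on their risk.

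A reader who sees similar days in both arms could take this as similar onset when the risk differs. A reader who sees different days could take it as earlier onset when only follow-up differs. At stake is the interpretability of a named safety variable. No power, error rate or sample size is involved.

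A smaller, related gap is the counting rule. Section 10.3.4 asks for a 7-day confirmatory analysis at any value above 2.0 mg/dL, with no exemption above 4 mg/dL. It also ends study treatment above 4 mg/dL, and 6.1 puts the Final Study Visit on the day after the last dose. How a patient without the 7-day sample counts is not stated.

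**Working it through.** **The plan's own figure.** 3 cohorts × 2 arms × 24 = 144, so 72 per arm (7.2.1). This reproduces. The protocol states no rate, effect size or power for PNALD/PNAC, so all rates below are assumptions.

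**Why the case-only day is insensitive.** When the hazard is low, event times among cases spread almost evenly over the observed period. With monthly samples on Days 30 to 360 and everyone followed to Day 365, the mean case day is close to (30 + 360)/2 = 195 whatever the risk. Simulation agrees: raising the true 365-day risk from 5% to 40% moves it only from about 194 to 180.

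**Main model (assumed).** Constant hazard h per 30 days, samples every 30 days, exit uniform over Days 90–365, and non-cases censored at their last sample. True risk at Day 90 is 1 − exp(−3h): 5.8% for h = 0.02, 8.6% for 0.03 and 11.3% for 0.04.

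*Risk doubles, same follow-up (72 per arm):*

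| Summary | h = 0.02 | h = 0.04 | Difference ÷ SE |
|---|---|---|---|
| Mean case day | 132 | 128 | 4.3/33.7 = 0.13 |
| Kaplan-Meier risk, Day 90 | 5.8% | 11.3% | 0.055/0.047 = 1.2 |
| Crude percentage | 13.1% | 24.3% | 0.113/0.065 = 1.7 |

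*Same risk (h = 0.03), mean follow-up 20 days shorter (exit to Day 325 instead of 365):*

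| Summary | Longer | Shorter |
|---|---|---|
| Mean case day | 130 | 118 (SE of difference 30) |
| Kaplan-Meier risk, Day 90 | 8.6% | 8.6% |
| Crude percentage | 18.9% | 17.3% |

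The crude percentage shifts by 1.6 points, against a 95% half-width for an arm difference of 1.96 × 0.065 = 12.7 points.

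**Other exit patterns.** If half the patients stay to Day 365, the doubling moves the mean case day from 166 to 160. In a model with a fixed 10% true 365-day risk and weaning after Day 90 at 0%, 10% or 30% per month, the mean case day is 192, 162 or 118. Across the assumed scenarios the expected number of cases per arm of 72 runs from about 1.5 to 28.5.

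**What a replacement must handle.** Visits are 30 ± 5 days (11.2.3), so many third samples fall after Day 90. With that window (uniform jitter assumed, h = 0.03), Kaplan-Meier read at Day 90 gives about 7.3% against a true 8.6%; read at Day 95 it gives about 8.8%. Final Study Visit samples also fall between monthly visits. Entered at their actual day, they push the curve at Days 365–366 to about 35–38% against a true 31%, depending on how the last days are handled. An interval-censored estimate gives 30.3% at Day 360 against a true 30.2%.

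**The case against.** **The SAP may settle it.** Section 7.2.3 defers methods and missing values to a SAP that is to be signed off before unblinding. The clause that follows the definition in 5.2 can be read as saying only which of two sample dates counts, and the list of statistics in 7.2.3 is given as examples. This stands: the case-only summary is a reading of the supplied text, and the absence of a rule there does not show that none exists.

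**The percentage already shows risk.** This also stands. A reader might infer that a case-only day would hide a doubled risk of PNALD/PNAC. The documents do not support that, because the same bullet in 5.2 reports incidence, which in the working responds at least as strongly as Kaplan-Meier at Day 90 (1.7 against 1.2 SE).

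**Nothing suggests that the arms will differ in follow-up.** The trial is randomised and double-blind, and a 12-day artefact with an SE of 30 is within the noise. This is fair. What is lost at this sample size is mainly information; a wrong conclusion from the artefact is unlikely.

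**Patients above 4 mg/dL need not be lost.** A reader might infer that the most severe cases go uncounted. Section 10.3.4 asks for the 7-day analysis at any value above 2.0 mg/dL, and 12.3.6 follows unresolved adverse events, so the sample may exist. Only the counting rule when it is missing is unstated. The shorter wording in 6.2, without a second sample, may simply abbreviate 5.2.

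What remains is that the variable, summarised as the supplied text describes, would not measure what its name says. In a purely descriptive study, that matters for this variable.

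**Conclusion.** The point holds in a limited form. On the supplied text, time to PNALD/PNAC would be summarised among cases only, under follow-up from below 90 to 365 days. Such a summary hardly moves when risk doubles (about 4 days, 0.13 SE) and moves more with length of follow-up (about 12 days for a 20-day gap). These sizes rest on an assumed constant hazard, monthly sampling and assumed exit patterns; other exit patterns change the days but not the conclusion.

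The incidence count and percentage remain valid on-treatment figures and should stay. The study is exploratory and unpowered, so no error rate or sample size is affected. This is a cheap improvement to one safety variable. Certainty is moderate because the SAP is not available.

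**What to change.** In the SAP, before unblinding:

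1. Keep the crude count and percentage.
2. In place of summary statistics of Study Day among cases, report the cumulative risk of a first qualifying value above 2 mg/dL. Give it by arm, and by age cohort where numbers allow (as 7.2.3 intends), with non-cases censored at their last bilirubin sample, 95% confidence intervals and numbers at risk.
3. Handle the sampling schedule explicitly. Either make an interval-censored estimate the main one, or assign samples to nominal visits and read the curve at the end of the visit window (for example Day 95 instead of Day 90).
4. Report 12-month risk only where enough patients remain at risk, and state that it assumes exit is unrelated to bilirubin risk.
5. Use one event definition for incidence and time. State how a patient counts when the 7-day sample is missing, and reconcile 6.1 and 10.3.4 on that sample after a value above 4 mg/dL. This is a counting rule only; no clinical rule is proposed.
6. Events per 100 patient-months and a competing-event figure are optional.

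**Cost.** Some wording and slightly more programming; the dates and results are already collected. Intervals will be wide. At an assumed 3% per month, the per-arm 95% half-width is about 7 points at Day 90. At Day 360 it is about 24 points if exit is uniform (about 1 of 72 still at risk), or 12 points if half the patients stay to Day 365 (about 26 at risk). If exit is related to risk, the 12-month Kaplan-Meier figure could be off by about −6 to +8 points under assumed correlations of −0.5 to +0.5 between risk and length of stay.

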## 6. Study Design

### 6.1 Description of the Study Design

This is a prospective, randomized, double-blind, parallel-group, active-controlled, phase 4 multicenter study to assess safety and efficacy of Smoflipid compared to Intralipid 20% in pediatric patients requiring long-term PN.

Treatment group 1: Smoflipid (investigational drug)

Treatment group 2: Intralipid 20% (control drug)

The study drugs, Smoflipid and Intralipid 20%, are lipid emulsions for infusion and will be provided in bags containing 100 mL, 250 mL, or 500 mL. Detailed information on packaging,

---

 In this study protocol, the terms PNAC and PNALD are used synonymously and are defined by direct bilirubin levels > 2 mg/dL.

## **Clinical Study Protocol SMOF-028-CP4**

### **Smoflipid® (lipid injectable emulsion)**

---

labelling, and dose of study drug is provided in Section 10.

The study population will be pediatric patients of 3 months to 16 years of age with indication for PN that is expected to continue for 90 days at minimum, as consequence of reversible or irreversible intestinal failure. This condition can be present in patients with, e.g., short bowel syndrome, intestinal atresia, abdominal surgical procedures due to gastroschisis or omphalocele closure, necrotizing enterocolitis, gastrointestinal motility disorder, or mucosal enteropathy. Study patients will be hospitalized or treated in the home care setting, and the study will also continue during transmission from hospital to home PN or during re-hospitalization. During the first 90 days, study treatment will last as long as PN is required to cover 60% or more of the patient's total energy requirement. Unless terminated in the first 90 days, study treatment will last as long as any PN including intravenous lipids is required, but at maximum for 1 year in total.

If a patient is found to be potentially eligible for participation in the study, a signed and dated informed consent form (ICF) will be obtained from the patient's parent(s) or legal representative(s) prior to the performance of any study-specific procedures or assessments. If possible, patient assent must also be obtained.

Randomization into the 3 age group cohorts will be distributed evenly so as to have 48 subjects in each age group with at least 23 subjects in each treatment group per cohort (see Section 6.3):

Randomization group 1: 48 patients 3 months to < 2 years of age

Randomization group 2: 48 patients 2 years to < 12 years of age

Randomization group 3: 48 patients 12 to 16 years of age

Before initiation of study treatment, demographics, including medical history, race and ethnicity, starting date and composition of current PN, current medications, physical examination findings, vital signs, body weight and length/height, BMI (> 2 years) and head circumference (< 3 years) will be documented, and blood samples will be obtained for the assessment of baseline laboratory values.

During the treatment phase, concomitant medications and all safety and efficacy parameters will be recorded according to the study schedule (see Section 11). All I.V. energy sources (study drugs, other PN components, propofol, dextrose from drug carrier solutions), enteral formulas, and oral intake will be documented daily to assure that total energy content from all sources does not exceed the prescribed caloric target. Changes in dosage of the study drugs or other PN components, and the reason for these changes will be recorded.

Study treatment will last for a minimum of 90 consecutive days and, as long as PN including lipids is indicated, up to 365 consecutive days. The study will be terminated if infusion of the study drug cannot be continued because of increased TG or direct bilirubin levels (see 10.3.4 Intravenous lipid dose management).

Up to Study Day 90 the study treatment will be terminated (i.e., early termination of study treatment) if less than 60% of the patient's energy requirements are provided by PN for at least

## **Clinical Study Protocol SMOF-028-CP4 Smoflipid® (lipid injectable emulsion)**

---

one month. If PN is still indicated after termination of the study treatment, it will continue per normal institution policy. Study drugs will no longer be used.

Between study Day 91 and Study Day 365, the study treatment will be terminated (i.e., late termination of study treatment) as soon as nutritional needs can be fully covered from enteral or oral nutrition, or is continued without a lipid emulsion (i.e., PN, or at least the lipid emulsion, is no longer indicated).

Whenever a patient has received his/her last dose of study drug, a Final Study Visit will be performed the following day to perform the end-of-study procedures. If after the last dose of study medication PN is still indicated, it will continue per normal institution policy.

To ensure safety of the patients during their study participation, medical monitoring will be performed on all safety relevant information collected during the trial. A medical safety officer will be available for safety related questions throughout the study.

### **6.2 Rationale of Study Design, Including Choice of Control Group**

The FDA requested that Fresenius Kabi perform a postmarketing study in pediatric patients 3 months to 16 years of age to evaluate the safety and efficacy of Smoflipid administered for at least 90 days, and continued for all patients who remain on PN for up to 1 year, compared to standard of care soybean oil based lipid emulsion (Intralipid 20%) administered for the same duration. Per the request of the FDA, the study's efficacy assessments will include anthropometric measures and evaluation of the risk of developing essential fatty acid deficiency (EFAD). Genetic polymorphisms in the fatty acid desaturase genes (FADS) FADS1 and FADS 2 should be determined in a subset of patients. The study's safety assessments will include evaluation of the risk of developing PNALD and PNAC. Plasma phytosterol levels will be included as well.

The current multicenter study to evaluate safety and efficacy of Smoflipid for nutrition in pediatric patients 3 months to 16 years of age was designed to meet Pediatric Research Equity Act (PREA) requirements, i.e. to provide:

- Evidence-based information on the correct dosing for these pediatric age groups,
- Evidence-based information on nutritional efficacy and
- Evidence-based information on pediatric safety issues as indicated by possible adverse events

Smoflipid and the comparator, Intralipid 20%, will be dosed according to each patient's caloric needs and clinical condition. The maximum lipid dosage for the age groups (see Section 10.3) is according to the US Prescribing Information for Intralipid 20%, i.e., for pediatric patients up to 3 g/kg/d, and up to 2.5 g/kg/d for adolescents according to maximum dosage for adults. The dose infused will be assessed for safety and efficacy in pediatric patients. The same maximum dosage for lipids in infants and children, i.e., 3 g/kg/day, applies for Smoflipid in countries

## Clinical Study Protocol SMOF-028-CP4 Smoflipid® (lipid injectable emulsion)

---

where the pediatric use is approved.

The specific outcome measures selected to evaluate nutritional efficacy in the current Smoflipid protocol are:

- Body weight and length/height and head circumference (patients < 36 months of age)
- Fatty acid profiles including linoleic acid,  $\alpha$ -linolenic acid, arachidonic acid, docosahexaenoic acid, eicosapentaenoic acid and Mead acid, analyzed in total plasma and in red blood cell membranes
- Triene/tetraene ratio (Holman Index) in total plasma to assess essential fatty acid deficiency (EFAD)

PREA requirements are designed to obtain evidence-based safety information on pediatric patients to help the prescribing physicians understand what adverse events can be anticipated. In the current study protocol, specific safety outcomes as listed below were selected to capture changes in standardized safety assessment, and safety assessment particularly referring to safety aspects of different parenteral lipid components:

- Number of patients in each treatment group with direct bilirubin levels > 2 mg/dL, (incidence of PNALD/PNAC)
- Time until reaching direct bilirubin levels > 2 mg/dL (time until developing PNALD/PNAC)
- Sterols in plasma including phytosterols
- Laboratory values
- Vital signs
- Adverse events
- The relation between genetic polymorphisms in the fatty acid desaturase genes FADS1 and FADS2 and plasma concentrations of linoleic acid,  $\alpha$ -linolenic acid, arachidonic acid, docosahexaenoic acid, eicosapentaenoic acid, and Mead acid, as well as relation to and EFAD (triene/tetraene ratio).

As Smoflipid and its components have been used widely and given world-wide with a very rare incidence of adverse drug reactions (ADRs)/serious adverse events (SAEs), no confirmatory hypotheses will be tested. All target variables will be analyzed in an exploratory manner presenting descriptive statistics. The trial will not be powered. To power this trial, selection of one single parameter would be required as a primary safety endpoint to show a clinically meaningful difference between the treatment groups (the treatment effect) in a reasonable sample size and trial duration. As mentioned above, both Smoflipid and Intralipid 20% provide parenteral lipids. Selecting a single parameter to power the study as a superiority study or as a non-inferiority study with a reasonable non-inferiority margin would be difficult because the similar treatment concept would require more patients than could be obtained under any reasonable circumstances due to very low incidence of adverse drug reactions.

